Vaping sessions will take place after collecting biospecimens and completing questionnaires on sociodemographics, tobacco use history, and dependence on ECs and cigarettes. Guided by study staff, participants will take two puffs of each of the 10 study conditions (5 freebase nicotine fractions \times 2 nicotine concentrations) using the study EC device, followed by a 10-minute washout period between conditions. During the washout period, participants will be instructed to rinse their mouths and spit three times with room-temperature water before sampling the next preparation to minimize carryover effects. The washout period was deemed sufficient based on an arterial study showing a return to baseline plasma nicotine levels 40 minutes following a 10-puff vaping session (hence, 4 minutes are needed for nicotine levels to return to baseline after each puff).²² Participants will be provided pre-filled and weighed e-liquid pods in random order. Participants will be instructed to inhale for at least 1 second for each puff, but other puffing parameters (i.e., flow rate, maximum puff duration, puff volume, rate of exhalation) will not be controlled.

After each condition, participants will complete General Labeled Magnitude Scale (gLMS)¹⁴ and Labeled Hedonic Scale²³ to rate the degree of liking or disliking of sensations and the strength of sensory attributes of e-liquids including throat hit, smoothness, harshness, sweetness, and bitterness. Participants will also rate overall acceptance on a tobacco industry-designed thermometer scale (from 0 "the very worst" to 100 "the very best", with 50 indicating "indifferent").²⁴ Drug Effects/Liking Questionnaire,²⁵ the modified Cigarette Evaluation Questionnaire (mCEQ), and the adapted version of behavioral intentions for continued use (from 1 "extremely unlikely" to 7 "extremely likely")²⁶ will also be collected to assess subjective responses to ECs (e.g., reward, satisfaction).²⁷

All study visits will take place at the OSUCCC's Center for Tobacco Research, where participants will complete a consent form, screening procedures, vaping sessions, and online questionnaires and surveys on a tablet.

C. Recruitment

1) Number of Participants

A total of 150 participants will be recruited, including young adult e-cigarette (EC) users with minimal or no history of smoking (n=75) and older adult smokers (n=75).

2) Participant Population

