The primary goal of the study is to identify a nicotine fraction limit that is appealing to smokers with a minimal appeal to young adult EC users. Generalized linear mixed models will be employed for measures of appeal (e.g., industry thermometer rating and sensory appeal metrics). Models will include demographic and smoking history as covariates, random effects for subject, main effects for user group (smokers vs. EC use), FB fraction (numeric), and concentration (categorical), and interaction effects between smoking group and each of the condition parameter variables (i.e., FB fraction and concentration). A significant interaction between smoking group and a condition parameter variable would indicate that the variable differentially affects appeal between the two user groups. Because of multiple measurements tested, we will assume a significance threshold of $p=0.01$. Conservatively, considering 120 participants, a correlation of 0.5, and $\alpha=0.01$, a two-sided paired t-test achieves 80% power to detect an effect size of 0.32 standard deviations of the measurement for the concentration main effect. For FB fraction, with 120 subjects, the model achieves 80% power to detect a slope of 0.31, considering $\alpha=0.01$. We estimate the power for the categorical interactions by pairwise comparisons of the two interacting groups (with two 2-level variables there are a total of 4 groups) and adjust the p-value to account for the 6 possible pairwise comparisons ($0.01/6=0.0017=p$). With 30 samples per group, a two-sided, two-sample t-test achieves over 80% power to detect a 1.7-fold difference between any of the two groups in the interaction term, considering $\alpha=0.0017$ and coefficient of variation=0.5. For interactions with FB fraction, group sizes of 60 achieve 80% power to detect a difference in slopes of 0.43, considering $\alpha=0.01$. Interactions between condition parameter variables will also be explored. Since our goal is to find combinations of the condition parameter that are appealing to smokers but not young adult EC users, we will compare condition combinations directly to identify the condition parameter combinations that result in the largest difference in appeal between

the two user groups. Carryover effects will be explored by estimating the interaction of a given condition with the preceding treatment and period effects tested by the interaction of treatment with order.

III. Data and Safety Monitoring Plan

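### Power for the user group by concentration interaction treats a within-person factor as four independent groups of 30 and uses a fold change that does not suit the thermometer or liking ratings

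*Combined protocol and SAP*

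**What the plan says.** Sections II.A and II.B describe a within-subject crossover in which each person samples all 10 conditions (five freebase, FB, fractions at each of two concentrations).

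Section II.E plans mixed models with a subject random effect. It reads a significant interaction between user group and FB fraction, or user group and concentration, as differential appeal. Power is then given on four different bases:

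- **Concentration main effect:** with 120 participants, correlation 0.5 and alpha 0.01, "a two-sided paired t-test achieves 80% power to detect an effect size of 0.32 standard deviations".
- **FB fraction main effect:** a detectable slope, with 120 subjects.
- **FB fraction interaction:** a difference in slopes, with 60 per user group.
- **Categorical interaction:** estimated "by pairwise comparisons of the two interacting groups (with two 2-level variables there are a total of 4 groups", with alpha divided by six. The result is: "With 30 samples per group, a two-sided, two-sample t-test achieves over 80% power to detect a 1.7-fold difference between any of the two groups", "considering $\alpha=0.0017$ and coefficient of variation=0.5".

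User group and concentration are the only two-level variables in the model, so the last item is the power statement for group by concentration.

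The outcomes named for these models are the thermometer rating and sensory appeal metrics. The thermometer runs from 0 (worst) to 100 (best) with a labelled neutral point at 50. The gLMS and the Labeled Hedonic Scale are used together "to rate the degree of liking or disliking of sensations" and the strength of sensory attributes (sections II.B and II.D.1). No mean or SD is given for any scale, and no outcome is named for the fold change.

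**The concern.** Three features of the categorical-interaction sentence do not match the design.

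1. **Cells.** Thirty per group is 120/4, as if each person belonged to one user group and received one concentration. In this crossover each person contributes to both concentration cells of their user group. The same paragraph recognises this when it uses a paired test for the concentration main effect.
2. **Contrast.** The planned test asks whether the concentration effect differs between user groups. A difference between two cells can arise from a main effect alone, with no interaction.
3. **Metric.** A ratio and a coefficient of variation (CV) need a meaningful zero. Zero on the thermometer is the worst rating, not an absence of appeal, and a liking/disliking rating has no natural zero for a ratio either.

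This is the only sensitivity stated for one of the two interactions that the plan will interpret as differential appeal. A reader who finds no group by concentration interaction could not use it to judge what size of effect the trial was able to exclude.

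**Working it through.** **Inputs (section II.E):** 120 participants, 60 per user group; correlation 0.5; two-sided alpha 0.01, and 0.01/6 = 0.0017 for pairs; CV 0.5; ratio 1.7; 30 per group. Power is from the noncentral t distribution.

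**1. The plan's own figure.** On the log scale, SD = √ln(1 + 0.5²) = √ln 1.25 = 0.472, and d = ln 1.7 / 0.472 = 1.123. With 30 per group (58 df, noncentrality 1.123 × √15 = 4.35) and alpha 0.0017, power is 84.8%. The 80% point is d = 1.07, a ratio of 1.66. The claim of over 80% reproduces. The log scale is not the only reading that does so. On the raw scale with a common SD of half the lower mean, d = 0.7/0.5 = 1.4 and power is 98.0%. With SD proportional to each mean, power is 72.1%.

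**2. The plan's paired figure.** The SD of a within-person difference is σ√(2(1 − 0.5)) = σ. With n = 120 and alpha 0.01, 80% power is reached at 0.316 SD, which matches the plan's 0.32. The plan therefore treats concentration as within-person there.

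**3. The six pairs.** Two user groups by two concentrations give four cells and six pairs. Two pairs (20 against 50 mg/mL within smokers, and within EC users) are the same people, so a two-sample test does not apply. The other four compare different people, with 60 on each side.

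**4. Two cells are not the interaction, even on the plan's own premise.** With four truly independent groups of 30, the interaction contrast has SE σ√(4/30) and 116 df. At alpha 0.01 it needs 1.27 SD for 80% power. At 1.123 SD its power is 68%.

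**5. The planned interaction.** Take each person's 50 minus 20 mg/mL difference, with SD σ√(2(1 − ρ)), and compare 60 smokers with 60 EC users at alpha 0.01. A two-sample test with 60 per group reaches 80% power at 0.633 SDs of that difference. In rating SDs, the detectable effect is 0.633 × √(2(1 − ρ)) for one rating per concentration. It is that value divided by √5 when the five FB levels are averaged under compound symmetry.

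| ρ | One rating per concentration | Five FB levels averaged |
|---|---|---|
| 0.3 (assumed) | 0.75 SD | 0.33 SD |
| 0.5 (plan) | 0.63 SD | 0.28 SD |
| 0.7 (assumed) | 0.49 SD | 0.22 SD |

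With the 75 per group that the protocol intends to recruit and ρ = 0.5, the values are 0.56 and 0.25 SD.

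**6. Between-people pairs with the right cell size.** At alpha 0.0017, 60 per group detect d = 0.74 (a ratio of 1.42 on the plan's log scale), against 1.07 with 30.

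**7. What 1.7-fold means on the thermometer.** From 20 it is 14 points (to 34), from 40 it is 28 (to 68), and from 50 it is 35 (to 85). Above 100/1.7 = 58.8 it exceeds the scale. Scoring in the opposite direction changes the ratio: 40 against 68 is 1.7-fold, but 60 against 32 is 1.875-fold.

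**The case against.** The calculation is correct on its inputs, so a reader who infers an arithmetic mistake would be wrong. The fault is a mismatch between the power basis and the planned test.

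The scale criticism also has limits. A neutral midpoint is stated only for the thermometer. The battery includes strength-of-sensation ratings, for which a ratio may be sensible. Section II.E allows transformations and specifies generalized linear mixed models, which can express ratio effects. It would be too strong to say that every appeal outcome is bipolar. What stands is narrower: section II.E names the thermometer as an outcome, does not confine the fold change to intensity ratings, and gives no mean or SD with which to convert it.

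Pairwise comparisons do have a place, because section II.E also plans to compare condition combinations directly between user groups. Pairwise power should therefore be corrected, not struck out.

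Finally, the primary goal is an FB fraction limit. The FB interaction has its own power statement, based on 60 per user group, and this point leaves it untouched. The 120-person basis is also below the 150 to be recruited. These facts limit the consequences, but they do not make the sentence right for the interaction that it describes.

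**Conclusion.** Wrong as written. The stated power belongs to a two-cell comparison in a four-arm parallel design, while the trial will test a difference between user groups in a within-person change. It also conflicts with the paired basis and the groups of 60 used in the same paragraph.

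On the plan's correlation, alpha and 60 per group, the interaction has 80% power at 0.63 SD from one rating per concentration, or about 0.28 SD when all five FB levels are used. The second figure assumes compound symmetry, with the correlation of 0.5 applying between single ratings. The ranges over ρ from 0.3 to 0.7 are assumptions.

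Two stronger readings are tempting and are not supported:

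- **That the trial is underpowered.** Treating the cells as independent groups of 30 understates the available information. The correct interaction test is probably more sensitive than the stated figure suggests.
- **That the gap can be given in thermometer points**, for example by setting 35 points (1.7-fold from 50) against the point equivalent of 0.63 SD. The documents give no thermometer SD, and deriving one from the CV would rely on the quantity in question. The two figures also differ in contrast, alpha and power level.

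**What to change.** Replace the categorical-interaction sentence in section II.E with one on this basis:

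> For user group by concentration, the within-person difference between 50 and 20 mg/mL is compared between 60 smokers and 60 EC users (correlation 0.5, two-sided alpha 0.01). Power is 80% for 0.63 SD with one rating per concentration (0.75 to 0.49 SD for assumed correlations of 0.3 to 0.7). It is 80% for about 0.28 SD (0.33 to 0.22 SD) when the five FB levels are averaged, assuming compound symmetry.

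In addition:

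- State the effect in SDs. Convert to scale points only with an SD labelled as an assumption.
- If a fold change is kept for intensity ratings, name those outcomes and the log-scale basis.
- If pairwise power is kept for the direct comparisons of condition combinations between user groups, base it on 60 per group (d = 0.74 at alpha 0.0017). State the number of comparisons behind the adjusted alpha.

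The cost is a few sentences in the SAP. Sample size, conditions, model and data collection do not change.

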In the proposed study, a sample of young adult (21-24 years) exclusive EC users with no or minimal history of smoking (n=75) and older adult (25-50 years) smokers (n=75) will complete a single-visit, double-blinded, within-subject randomized crossover trial. Participants will vape e-liquids containing varying freebase (FB) nicotine fractions (5, 25, 45, 65, 85%) at 20 or 50 mg/mL concentrations. The FB fractions were selected to cover a wide range with the lower end consistent with JUUL and disposable pod-based ECs that are popular among youth¹¹ and the higher end resembling early ECs that were FB nicotine-based and less appealing to young people. Each of the 10 conditions will be tested in a 2-puff session, followed by rating the appeal and sensory attributes, with a 10-minute washout period between conditions. Previous studies used a similar study design to examine the appeal of EC flavors, nicotine concentrations, and interactive effects of flavor and nicotine.¹²⁻¹⁵ For example, in a study of young adult current EC users,¹² the sensory appeal of ECs decreased as nicotine concentration increased but was not affected by flavoring. Another study of current EC users or smokers reported higher ratings of appeal for salt nicotine vs. free-base nicotine across different flavors, and salt nicotine decreased perceived harshness more among never smokers than ever smokers.¹⁵ While these studies shed light on the effect of nicotine salts and concentration on the sensory experience of EC use, their design was limited in ability to evaluate the effect of granular fractions of nicotine salts. This study will fill the gap in the literature by examining the effect of five free-base levels of nicotine at two nicotine concentration levels and determining the 'sweet spot' level of free-base nicotine that can be tolerated by smokers but not by non-smokers.

B. Study Procedures

Participants will be screened initially through an online screener, which will be linked to our study advertisement and administered using REDCap. Eligible participants interested in participating will be scheduled for the study visit via phone or e-mail. Participants will be instructed that they must remain nicotine abstinent for 12 hours before their visit and will receive a reminder the evening before.

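### The plan looks for the largest group gap in appeal among ten conditions but states no uncertainty or correction for that selection, and does not say how the gaps are estimated

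*Combined protocol and SAP*

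**What the plan says.** Section II.E (Data Analysis) sets the target: "The primary goal of the study is to identify a nicotine fraction limit that is appealing to smokers", while holding little attraction for the young EC users. Section II.A describes the same aim as finding the "level of free-base nicotine that can be tolerated by smokers but not by non-smokers". The candidates are ten conditions, "varying freebase (FB) nicotine fractions (5, 25, 45, 65, 85%) at 20 or 50 mg/mL concentrations".

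The only step in II.E that turns the data into a choice among conditions is this one: "we will compare condition combinations directly to identify the condition parameter combinations that result in the largest difference in appeal between" smokers and young EC users.

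The model named earlier in the section is a mixed model with free-base fraction as a numeric term, concentration as a categorical term, and an interaction of user group with each. The section does not say whether the gaps to be compared are cell means or estimates from this model.

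Two multiplicity provisions appear. The 0.01 significance threshold is justified by the number of outcome measures. The 0.01/6 adjustment belongs to the power estimate for an interaction of two 2-level variables. Neither concerns selection among ten conditions.

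**The concern.** The largest of several noisy estimates tends to be too large, because selection favours cells whose error happened to be positive. If the same data choose the condition and estimate its gap, the estimate is biased upward and an ordinary interval covers less often than its label says. Neighbouring fractions can also swap places by chance.

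The results are meant to inform product regulation, including a possible minimum free-base fraction. A near-tie between two or three fractions could be read as a threshold, with a gap between young EC users and smokers larger than the true one. Nothing in II.E would show the reader whether the choice is firm or close.

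**Working it through.** **Inputs from the documents.** Ten conditions (II.A); 75 per group recruited (II.C); power based on "considering 120 participants, a correlation of 0.5" and, for interactions with fraction, groups of 60 (II.E).

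**Assumptions.** Ratings have unit SD in both groups and the same correlation between all pairs of conditions; covariates are ignored. The true gap profiles are assumed, since the documents give none.

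**The plan's own figure.** The plan gives no figure for the selection step. Its detectable concentration effect does reproduce. The SD of a paired difference is √(2(1−0.5)) = 1, so the normal approximation gives (2.576 + 0.842)/√120 = 0.312. By noncentral t, power at 0.32 SD is 0.811.

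**Standard error of one gap.** √(2/n) = 0.163 SD at n = 75 and 0.183 SD at n = 60.

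**Equal true gaps, analytically.** The expected maximum of ten independent standard normals is 1.539. Only the non-shared part of the error drives selection, so the bias is 1.539 × √(1−0.5) × √(2/n):
- n = 75: 1.539 × 0.707 × 0.163 = 0.178 SD
- n = 60: 1.539 × 0.707 × 0.183 = 0.199 SD

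At n = 75 the bias is 0.21 SD if the correlation is 0.3 and 0.14 SD if it is 0.7.

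**Simulation, gaps compared as cell means.** Ten correlated normal gaps, 200,000 sets, same profile at both concentrations, n = 75, correlation 0.5:

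| True gap from 5% to 85% (SD) | Bias (SD) | Coverage of nominal 95% interval | Fraction chosen |
|---|---|---|---|
| Equal everywhere | 0.18 | 86% | each level 20% |
| 0, 0.2, 0.4, 0.4, 0.4 | 0.15 | 89% | 45, 65 and 85% about one third each |
| Linear, 0 to 0.4 | 0.12 | 91–92% | wrong 26% |
| Linear, 0 to 0.8 | 0.08 | 94% | wrong 7% |

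With 60 per group the biases run from 0.10 to 0.20 SD. For a peak of 0.4 SD at 65%, the bias is about 0.11 to 0.12 SD and the wrong level is chosen about 20 to 30% of the time, depending on how sharply the gap falls away. For example, 0, 0.13, 0.27, 0.40, 0.20 gives 21%.

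**Same sets, gaps fitted as linear in fraction plus a concentration term.**
- Equal gaps: bias 0.07 SD, coverage 93.6%, choice split between 5% and 85%.
- Linear 0 to 0.4 or 0 to 0.8: bias 0.03 SD, coverage 95%, 85% chosen essentially always.
- Plateau: 85% chosen essentially always, bias 0.11 SD, coverage 88%.
- Interior peak at 65%: the peak is never chosen.

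The last result needs no simulation. A straight line in fraction has its maximum at one end of the range. Adding the exploratory interaction between fraction and concentration still leaves a straight line at each concentration.

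**Steep gaps.** Read the plan's detectable slope difference of 0.43 as SD per SD of fraction (the units are not stated). The SD of the five levels is 28.3 points, so the gap changes by 0.43 × 80/28.3 = 1.2 SD across the range. Cell-mean bias is then 0.02 to 0.08 SD and the right level is chosen 96 to 99% of the time. At half that slope the figures are 0.05 to 0.11 SD and 78 to 87%. These ranges cover 60 and 75 per group, with no concentration effect or one of 0.32 SD.

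**The case against.** The strongest reply has four parts.

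**The text does not say that one winning cell becomes the limit.** It speaks of combinations in the plural, and the goal has two parts: appeal to smokers and little appeal to young EC users. A reader might infer that a single fraction will be announced with its observed gap; the documents do not say so. This stands. But no rule says which conditions count as tied with the largest.

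**Cell means are an assumption.** The only estimator named is the model with numeric fraction, under which most of the bias and instability disappears when the truth is linear. This stands, and it is why the point is conditional. It exchanges one problem for another: that model cannot place the optimum inside the range, although II.A looks for a sweet spot.

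**The equal-gap case is extreme.** With equal gaps there is no group-by-fraction interaction, so the test at 0.01 would be non-significant about 99% of the time, and no fraction is wrong. The plateau choices are also equally good on this criterion. Both remarks stand; the equal-gap figure marks the upper end of the bias. But the plan does not make the comparison depend on the interaction test.

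**A concentration effect reduces the bias.** Adding 0.3 SD at one concentration lowers it from 0.12 to 0.08 SD in the linear 0 to 0.4 case. True, but it leaves fewer cells in which the best fraction can win: at half the powered slope with 75 per group, a 0.32 SD concentration effect lowers the chance of the right level from 87% to 82%.

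**Conclusion.** The concern holds in conditional form. Section II.E selects on the largest gap among ten conditions in service of the primary goal, and attaches no uncertainty to the selection.

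With cell means, the reported gap would be expected to be too large by about 0.08 to 0.18 SD at 75 per group, or 0.10 to 0.20 SD at 60, across the flat, plateau and linear profiles. The rating SD is not given; at an assumed 20 to 30 thermometer points, 0.178 SD is 3.6 to 5.3 points. The chosen fraction is unstable when the gap is flat, shallow or peaked inside the range, and fairly stable when it is steep.

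A reader might conclude that the gap will be materially overstated and the fraction unreliable whatever the data show. The documents do not support that: the size depends on the unknown profile and on an estimator that the plan leaves open. All figures rest on unit-SD normal ratings and one common correlation.

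**What to change.** In II.E:

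1. State that the conditions will be compared using a model with free-base fraction as a categorical factor, including its interactions with user group and with concentration. The numeric-fraction model can remain for the slope tests.
2. Bootstrap participants within user group, rerun the whole selection each time, and report how often each condition is chosen, with a selection-adjusted interval for the gap (bias-corrected or simultaneous).
3. Report the set of conditions not separated from the largest. Do not name a single fraction when that set holds more than one.

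This needs SAP wording and a short program, with no new participants, visits or data. The price is precision. At the plan's 0.01 level and correlation 0.5, a simultaneous critical value over the ten gaps is 3.25 against 2.58, so with 75 per group the half-width rises from 2.58 × 0.163 = 0.42 SD to 3.25 × 0.163 = 0.53 SD. The reported gap will be smaller, and the answer may be a range of fractions. If the gap is steep, the bootstrap will show one dominant fraction and little is lost.

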Similarly, e-cigarette (EC) manufacturers manipulate nicotine dimensions, including concentration and form. These manipulations have increased palatability and nicotine delivery, leading to increased appeal and addictiveness, particularly among young people. While ECs pose less risks to smokers who completely switch from cigarettes to ECs, EC use among young people is alarming. Regulating nicotine can potentially make products unappealing to young people while still providing smokers with a less harmful alternative with sufficient satisfaction. The overall aim of the proposed study is to determine if an EC product standard requiring a minimum level of free-base nicotine (nicotine form) would reduce the appeal of ECs for young adults but not older adult smokers who are more accustomed to the harshness of free-base nicotine. A single-visit, double-blind, randomized crossover design will be used, where young adult exclusive EC users with minimal or no history of smoking and older adult smokers complete EC puffing sessions and assess outcomes of appeal and sensory experience, using e-liquids that differ by 2 nicotine concentrations and varying free-base nicotine fractions. The study will be the first to examine the impact of nicotine dimensions on EC abuse liability and determine whether regulations limiting free-base nicotine fraction in EC liquids are appropriate for public health. Results will inform marketing and product regulations that reduce appeal in young people who do not smoke but not in adult tobacco users.

B. Background

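### The selection step looks for the largest between-group difference in appeal, but the goal concerns the level of appeal in each group, and no smoker floor, young-user ceiling or 'none qualifies' outcome links the two.

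*Combined protocol and SAP*

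**What the plan says.** Section II.E gives the primary goal as to "identify a nicotine fraction limit that is appealing to smokers with a minimal appeal to young adult EC users". This sets a requirement on the level of appeal in each group. The opening summary (before Background) does the same: regulating nicotine could "make products unappealing to young people while still providing smokers with a less harmful alternative with sufficient satisfaction". Objectives (I.C) and Design Overview (II.A) repeat the two-part aim in other words, and none of these places gives a number.

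The selection step comes near the end of II.E. The goal there is conditions that "are appealing to smokers but not young adult EC users, we will compare condition combinations directly", and the comparison is made to "identify the condition parameter combinations that result in the largest difference in appeal between" the two user groups.

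The inferential part of II.E rests on group-by-condition interactions. A significant one "would indicate that the variable differentially affects appeal between the two user groups". Selection is not made conditional on that test. Appeal measures are listed as examples, and no single one is named for selection. The thermometer described in II.B runs from 0 to 100 with 50 as 'indifferent', but the selection step does not use that anchor.

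**The concern.** The goal and the criterion in the selection sentence are not equivalent. 'Appealing to smokers and not to young users' is a statement about two levels. 'Largest difference' is a statement about one contrast, and a contrast keeps its value when both groups move up or down together. A maximum over 10 conditions also always exists, so the step has no way to conclude that no condition meets the goal. The interaction test does not fill the gap, because it too concerns differences.

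The free-base (FB) limit is the trial's main product and is meant to inform product regulation. If the hypothesis in I.C holds only in part, the step as written could put forward a condition that smokers do not accept as a substitute, or one that young users still find attractive. The fitted models can supply each group's level, but the plan does not say that level enters the selection or is reported beside it. If limits are left until the results are in, they can be chosen to suit them.

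**Working it through.** **The plan's own figure.** There is none for this step: no error rate, power or sample size is attached to the selection. The power figures in II.E concern main effects and interactions and do not bear on it.

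**Step 1: a table of means.** These hypothetical thermometer means only show that the two criteria can disagree.

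| FB % | 5 | 25 | 45 | 65 | 85 |
|---|---|---|---|---|---|
| Smokers, 20 mg/mL | 62 | 61 | 60 | 56 | 52 |
| Young users, 20 mg/mL | 70 | 62 | 48 | 45 | 40 |
| Difference | -8 | -1 | 12 | 11 | 12 |
| Smokers, 50 mg/mL | 60 | 58 | 54 | 48 | 40 |
| Young users, 50 mg/mL | 72 | 60 | 44 | 30 | 14 |
| Difference | -12 | -2 | 10 | 18 | 26 |

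The largest difference is 40 - 14 = 26, at a condition smokers rate below 50. With an example floor (smokers at least 50) and ceiling (young users below 50), four conditions qualify: 60 vs 48, 56 vs 45, 52 vs 40 and 54 vs 44. Their largest difference is 12, and the condition with the difference of 26 is not among them.

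**Step 2: how often this would happen.** Inputs:
- 75 per group (II.C) and within-subject correlation 0.5 (II.E, used there for the paired test).
- SD 25, all means, and the limits of 50: assumed.
- Profiles are linear in FB from 5% to 85%, written as start-end at 20 mg/mL / start-end at 50 mg/mL.
- Each group mean is the true mean plus a subject part shared over the 10 conditions and a condition-specific part. Each part has standard error sqrt(0.5) × 25 / sqrt(75) = 2.04.
- Difference rule: largest smoker-minus-young estimate. Floor-and-ceiling rule: smoker estimate at least 50 and young estimate below 50, then the lowest young estimate, else none.

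One cell by hand: smokers 62-54 / 62-48, young users 62-35 / 62-15. At 50 mg/mL and 85% FB the true difference is 48 - 15 = 33. At 65% FB it is 51.5 - 26.75 = 24.75. The lead is 8.25. The standard error of a difference between two conditions' group differences is sqrt(4 × 0.5 × 25² / 75) = 4.08. Then 8.25 / 4.08 = 2.02, about 98% on the normal scale. That is how often the condition with a true smoker mean of 48 beats its nearest rival, and simulation gives the same 98%.

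Share of runs in which the difference rule names a condition with true smoker mean below 50:

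| Young users | Smokers 62-54 / 62-48 | Smokers 62-52 / 62-46 | Smokers 62-50 / 62-40 |
|---|---|---|---|
| 62-35 / 62-15 | 98% | 97% | 99% |
| 62-40 / 62-30 | about 75% | 72% | 47% |
| 62-45 / 62-35 | 67% | 62% | 39% |
| 62-50 / 62-40 | 54% | 45% | 20% |
| 62-35 at both | 5% | 5% | 0.3% |

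With young users at 62-48 at both concentrations the rate falls as low as 0.1%. With smokers flat at 60 and the steepest young-user decline it is 0%.

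**Step 3: failing either limit.** Over these 18 combinations (3 smoker × 6 young-user profiles), the difference rule names a condition failing the floor or the ceiling in 0.5 to 100% of runs. The floor-and-ceiling rule does so in 0.5 to 46%. It is lower in nearly all. The clear exception is smokers 62-54 / 62-48 with young users 62-35 at both concentrations: about 12% against 5%.

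**Step 4: no qualifying condition.** With smokers flat at 40, every condition fails a floor of 50, so any condition the difference rule names fails. With the steepest young-user decline, the floor-and-ceiling rule returns 'none' in 99.9% of runs.

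**The case against.** The strongest defence is that the sentence states its goal in words, speaks of combinations in the plural and of comparing them directly, and follows "Interactions between condition parameter variables will also be explored". On that reading it describes a comparison, not an automatic pick, and an analyst would see the group means. Under the hypothesis in I.C, with smokers unaffected and their appeal sufficient, the two criteria agree. This stands in part. The hypothesis case is conceded, and the single automatic pick simulated above is a literal reading. But the goal clause is never turned into a criterion, and the only criterion given ignores level.

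Four stronger readings are tempting and are not supported:
- *The direction of the difference is open.* The goal clause fixes it: smokers higher.
- *The step will usually pick a condition smokers dislike.* With the steepest young-user decline and a floor of 50, the rate for the falling smoker profiles stays between 87 and 99.9% over 60 or 75 per group, SD 20 to 30 and correlation 0.3 to 0.7. That can look robust, but the young-user profile is the main unknown, and changing it moves the rate to 0.1 to about 75%.
- *Naming a condition in every run is an error rate.* It is true of any maximum. It shows only that a 'none' outcome is missing.
- *Linear FB makes an interior 'sweet spot' unselectable.* That follows only if fitted values from the numeric-FB model are compared. Comparing condition means is the more natural reading of a direct comparison.

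The floor-and-ceiling rule is also not better everywhere, and 50 is only an example.

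**Conclusion.** The concern holds in this form: II.E sets a goal about levels in two groups, its only stated selection step is a difference, and no section supplies a smoker floor, a young-user ceiling or a 'none qualifies' outcome. That much follows from the text and needs no assumption.

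The size is not known. It depends mainly on how far each group's appeal falls with FB and on where the limits sit, and the documents give neither. The illustrative rates show that the mismatch can range from negligible to nearly certain, and they are not a forecast. The criteria can part if smokers' appeal also falls with FB or is low throughout, or if young users' appeal stays high. The data and models remain usable, so this should be fixed in the SAP and is not a flaw in the design.

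**What to change.** 1. Name one appeal measure for the selection.
2. Prespecify that a condition is selected only if the smoker mean meets a floor and the young-user mean is below a ceiling, both justified by the sponsor. The thermometer's 50 is one example for either. The aim in II.A of a level smokers can tolerate might justify a lower floor.
3. Among qualifying conditions, choose by the largest smoker-minus-young difference or by the lowest young-user mean. State which, because the choice can change the error rate. Allow 'none qualifies'.
4. Base the selection on the 10 condition means per group, with FB as a 5-level factor crossed with concentration and group. Keep linear FB for the trend and interaction tests.
5. Report both groups' means and the difference for all 10 conditions with simultaneous intervals, and show how the selection changes over a range of floors and ceilings.

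The cost is SAP wording and a few model terms, with no new data. There are three downsides:
- Per-condition estimates are less precise than a fitted line.
- The result can be 'none' when a condition truly qualifies. With limits of 50 this occurs in 14% of runs if smokers are flat at exactly 50, and in 19% if smokers are flat at 60 and the only qualifying young-user mean is 48.
- Errors remain when a true mean lies near a limit, since one condition mean has a standard error of 25 / sqrt(75) = 2.9 under the assumed SD. Occasionally they exceed those of the plan's rule.
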